Figure 1 shows the response so far in the ongoing CervISA study to common microbial antigens and to HPV16 E6/E7 before and at two time points after ISA101 vaccination, expressed as median specific spots in the validated Interferon- γ ELISPOT assay. The baseline response to HPV16 E6/E7 is weak or not demonstrable before ISA101 vaccination, whereas the control response to common microbial antigens (Candida Albicans, PPD, Tetanus toxoid), the so-called memory mix (MRM) is robust. Chemotherapy alone causes a slight increase in the spontaneous T cell response to HPV16 E6/E7 and a marked increase in the T cell response to the MRM (data from visit 4, just before the first ISA101 vaccine dose). At visit 8 (after 2 vaccine doses) and at visit 10 (after 3 vaccine doses), robust vaccine-induced T cell responses to HPV16 E6/ E7 are evident. The data indicate that the immune response to the 40 µg and 100 µg cohorts is quite strong, responses to 20 µg/peptide being lower. These responses, like in the pilot study,¹² were again substantially higher than in a previous study in the same category of patients without timing of vaccination with respect to chemotherapy cycles²⁰. Moreover, the data indicate that the immunologic responses were at least the same high levels of T cell immune response against HPV16 E6/E7 in many patients as in previous complete clinical responding patients with premalignant high grade VIN disease¹¹ (van Poelgeest et al. 2016).

The combined immunological and clinical results indicate that in patients with pre-malignant disease more robust immune responses are induced than in patients with cervical cancer. This appears to be due to the abnormally high numbers of myeloid derived suppressor cells in the systemic circulation in patients with cancer as shown in the pilot study¹². In this study, all of 18 patients with advanced cervical cancer (recurrent or metastatic) had elevated levels in PBMC of immunosuppressive myeloid cell populations. A first cohort of 6 patients receiving standard carboplatin

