- 2) Paired analysis of immune-inflammatory markers in tumor and tumor infiltrating lymphocytes in pre- and post-treatment biopsies. Changes in immune-inflammatory markers will reflect immunomodulation by concurrent cisplatin and IMRT, the standard of care for this patient population. Immune-inflammatory markers will include: A) IHC or immunofluorescence to include: CD3, CD8, CD45RO, CD4/FOXP3, PD-L1 (co-stain on Macs), Ki-67; location of cells. B) RNAseq will be done where fresh-frozen tumor is

available.

- 3) Specific immunophenotypic and functional comparison of HPV-16 E6/E7 specific T cells responses using tetramer (for ~ 50% of enrolled patients who express HLA-A2.1), or overlapping E6/E7 peptides, using flow cytometry and IFN γ ELISPOT or cytolytic assays. Analyses will compare HPV specific vs bulk T cell phenotypes and function.
- 4) Seropositivity (circulating antibodies) and cytokines. Circulating antibodies against HPV E6/E7 and other viral tumor antigens, and circulating cytokines will be analyzed using multiplex (Luminex) ELISA assays.
- 5) Paired analysis of peripheral blood immune-inflammatory markers pre- and post-treatment with pembrolizumab. Markers will include: multi-color flow cytometry, including T cell activation panel, NK cells, myeloid-derived suppressor cells (MDSC), Treg subsets, phenotypic subsets, expression of PD1 and other co-stimulatory/co-inhibitory markers on these specimens.
- 6) Paired analysis of TCR clonality will be conducted in pre- and post-treatment TILs.
- 7) Next generation sequencing (exomes) for genomic epitope mapping with HLA allelic typing. Further detail is given in Section 9.4.5.

Summary of Rationale

- Data from the RTOG 0522, inclusive of the patients who meet the eligibility criteria for this trial, indicates that 30-40% of patients with intermediate risk, local-regionally advanced HPV+ HNSCC will experience disease progression within 5 years of CRT. Novel therapeutic approaches are needed to improve disease control (Ang 2010, O’Sullivan 2013).
- Anti PD-1 targeted therapy (pembrolizumab, Merck Inc.) demonstrated activity in metastatic recurrent HNSCC, with a response rate of 20% in patients with HNSCC (Seiwert 2014) Eligibility criteria included 1% or greater PD-L1 expression on tumors. Response rates were different for patients with high versus low PD-L1 expression (45% versus 11%).

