5. TREATMENT PLAN

The first ISA101b vaccine will be initiated 2 weeks prior to cisplatin-IMRT, and one week prior to the first dose of pembrolizumab. Vaccines will continue for 2 additional administrations at weeks 2 and 5, +/- 1 days from the successive pembrolizumab infusions. Pembrolizumab will be initiated 1 week prior to cisplatin-IMRT at the dose of 200 mg IV q3 weeks (+/- 3 days). Pembrolizumab will be continued concurrently through cisplatin-IMRT (weeks 2, 5, and continued for a 42 week maintenance period after completion of cisplatin-IMRT for a total pembrolizumab treatment period of 50 weeks (17 doses). NOTE: Per discretion of the treating investigator, the week 8 dose of pembrolizumab may be delayed up to 3 weeks for recovery of acute toxicities from chemoradiotherapy. This dose would be considered delayed, and all subsequent doses would be administered at a q3 week interval (+/- 3 days) until completion.

Table 2. Treatment Plan

- **IMRT 70 Gy (35 fractions, 2Gy/fraction)**
- **Cisplatin 100 mg/m² q21 days X 2 doses**
- **Pembrolizumab 200 mg q3week IV (flat dose) X 17 doses**
- **ISA10b Vaccine (Three vaccinations given 2 weeks prior to CRT and one week prior to pembrolizumab, then in weeks 2 and 5 during CRT on the same days (+/- 1 day) as pembrolizumab)**
- **PD-L1 status will not be used during this trial for treatment decisions**

Patients will be administered pembrolizumab 200 mg q3 weeks starting week -1 for a total of 17 doses.

Table 2.	Week of Treatment									
	-2	-1	0	1	2	3	4	5	6	8-47
IMRT			X	X	X	X	X	X	X	
Cisplatin			X			X				
Pembrolizumab **		X			X			X		X
ISA101b	X				X*			X*		

*ISA101b may be administered +/- 1 day of pembrolizumab administration for Weeks 2 and 5.

**Pembrolizumab 200mg IV q 3 weeks is given starting week -1 and continued for a total of 17 doses.

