9. BIOMARKER, CORRELATIVE, OR SPECIAL STUDIES

9.1 Biomarker Sampling Schedule

Table 10. Biomarker Sampling Schedule						
Collection timing	Serum	PBMC		Tumor Tissue	Whole Blood	
Study Day	Soluble Biomarkers	Immuno-phenotyping	Ex vivo Functional Assay	Tumor Biopsy	Gene Expression	SNP

Baseline (with biopsy, prior to registration)	X	X	X	X		X	X
Week -2, Week -1, CRT Weeks 0-3, Week 5, Week 7	X	X	X				
Optional biopsy: Week 1, Week 2				X			
Prior to every third maintenance pembrolizumab treatment (C4, 7, 10, 13, 16)	X	X					
Long term follow up	X	X					
At Progression, if applicable	X	X	X			X	

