10. STATISTICAL METHODS

This is a single arm phase 2 trial evaluating the efficacy of the addition of the ISA101b to pembrolizumab plus standard cisplatin-RT in intermediate risk HPV-16+ PULA HNSCC. This study is being performed in order to evaluate the oncologic efficacy of ISA101b with pembrolizumab and CRT and to characterize the safety profile of the combination.

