10.4 Proposed Data Analysis

At study completion a one-sided one sample exponential test will be conducted to detect an increase above the presumed historical control rate of 65% PFS at two years. If this test is rejected at $\alpha = .10$, the treatment regimen will be considered sufficient for further investigation. Probabilities of times to local recurrence, regional recurrence and death will be estimated by the Kaplan-Meier method with 95% confidence intervals as well as by cumulative incidence if needed to adjust for the competing risk of death. Treatment-related toxicities will be summarized by frequency and grade. If intervening deaths are observed cumulative incidence plots and analysis of competing risks may be conducted.

A series of correlative studies will be conducted based on blood and tissue samples collected prior to treatment among patients treated with pembrolizumab + ISA101b. The first item below is a planned analysis with alpha spending of 10% to be distributed among the biomarker endpoints.

1. Test the association of baseline H score of PD-L1 tumor expression, circulating antibodies against HPV, EGFR and p53 and other tumor antigens upon PFS using proportional hazards regression adjusting if needed for confounding variable such as T stage, N stage and smoking history.
2. Estimate and test the effect of ISA101b using paired (pre/post pembrolizumab +/- ISA101b) values of immune and inflammatory makers will be compared with the Wilcoxon test.
3. Compare differences in circulating HPV, EGFR, p53 and other tumor antigen antibodies using baseline versus 3-6 weeks or 6 months post-treatment. Linear mixed effect models will be used to evaluate the longitudinal response.
4. Estimate and characterize sequential series of blood samples pre- and post-treatment for a series of immune and inflammatory markers. These will be specified by the investigator and due to exploratory nature of these additional tests, p values will be adjusted for false discovery.

The change in CD4, CD8, FOXP3, PD-1, PD L1, and PD-L2 over time will be described graphically. An exploratory analysis of the relationship between those changes and PFS will be conducted by proportional hazards regression.

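### Section 10.4, item 2, labels as an ISA101b effect a within-patient change that also contains pembrolizumab and, once chemoradiation starts, cisplatin and IMRT

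*Combined protocol and SAP*

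**What the plan says.** Section 10.4 lists four correlative analyses. Item 2 is the only one said to estimate and test an ISA101b effect: "Estimate and test the effect of ISA101b using paired (pre/post pembrolizumab +/- ISA101b) values of immune and inflammatory makers will be compared with the Wilcoxon test". It names no pre visit, no post visit, no alpha and no sample size; the 10% alpha mentioned just before the list is reserved for item 1. The lead-in restricts these studies to "blood and tissue samples collected prior to treatment among patients treated with pembrolizumab + ISA101b", and section 10 opens with "This is a single arm phase 2 trial evaluating the efficacy of the addition of the ISA101b to pembrolizumab plus standard cisplatin-RT". There is therefore no group without the vaccine.

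The schedule is in section 5: "The first ISA101b vaccine will be initiated 2 weeks prior to cisplatin-IMRT, and one week prior to the first dose of pembrolizumab". Vaccine doses 2 and 3 follow at weeks 2 and 5, with pembrolizumab and during chemoradiation. Table 10 (section 9.1) schedules a baseline blood draw before registration and then draws at "Week -2, Week -1, CRT Weeks 0-3, Week 5, Week 7". Section 1.8 describes the blood comparison as "Paired analysis of peripheral blood immune-inflammatory markers pre- and post-treatment with pembrolizumab".

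**The concern.** The stated target is the vaccine, but the pairing is built around a different drug. Without a comparator arm, only the choice of time window can separate ISA101b from the rest of the regimen, and a window that ends after pembrolizumab cannot do so. If item 2 is followed as written, a regimen-level change will be reported under the vaccine's name. At stake is the reading of the only test in section 10.4 assigned to ISA101b, including any claim of vaccine activity carried forward to a later trial.

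**Working it through.** **1. What each blood pair contains.** Inputs are the dosing weeks in section 5 and Table 2 (ISA101b -2, 2, 5; pembrolizumab -1, 2, 5; cisplatin 0, 3; IMRT 0 to 6) and the draw weeks in Table 10. I assume each draw precedes dosing in the same week; Table 10 does not say so.

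| Pair (weeks) | ISA101b in interval | Pembrolizumab | Cisplatin / IMRT | ISA101b before the pre sample |
|---|---|---|---|---|
| -2 to -1 | dose 1 | none | none | none |
| -2 to 0 | dose 1 | yes | none | none |
| -1 to 0 | none | yes | none | dose 1 |
| -1 to 2 | none | yes | both | dose 1 |
| -2 to 3 | doses 1, 2 | yes | both | none |
| -2 to 7 | doses 1, 2, 3 | yes | both | none |
| 2 to 3 | dose 2 | yes | IMRT | dose 1 |
| 5 to 7 | dose 3 | yes | IMRT | doses 1, 2 |

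Only week -2 to week -1 contains ISA101b and no other study agent; the baseline draw can stand in for week -2. That pair ends before pembrolizumab, so a pre/post-pembrolizumab definition excludes it. No scheduled pair isolates dose 2 or dose 3.

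**2. Does the protocol expect the other agents to move the markers?** Yes. Section 9.4.3 expects activated T cells to rise after pembrolizumab. Section 1.8 says changes in the tumor markers will reflect cisplatin and IMRT. Section 1.7 reports from the cervical cancer study: "Chemotherapy alone causes a slight increase in the spontaneous T cell response to HPV16 E6/E7 and a marked increase in the T cell response to" a recall-antigen mix. That last source is indirect, because the chemotherapy was not cisplatin-IMRT.

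**3. Illustration of false attribution.** Item 2 gives no figure to reproduce. I take n = 45 from section 10.2 (evaluable patients) and assume a two-sided 5% test and normal paired differences with SD 1. The statistic W is the sum of ranks of the positive differences. With no change, its mean is n(n+1)/4 = 45 × 46/4 = 517.5 and its SD is √(45 × 46 × 91/24) = 88.6. The test rejects if |W − 517.5|/88.6 > 1.96. Simulation with 20,000 runs, zero ISA101b effect and an assumed shift from the other agents:

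| Shift (SD) | 0 | 0.1 | 0.2 | 0.3 | 0.5 |
|---|---|---|---|---|---|
| Rejection, n = 45 | 4.9% | 9.7% | 24.7% | 48.5% | 89.3% |
| Rejection, n = 30 | 5.1% | 8.0% | 18.5% | 34.5% | 73.4% |

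Hand check at 0.3 SD: E(W) = 45 Φ(0.3) + 990 Φ(0.3√2) = 45 × 0.618 + 990 × 0.664 ≈ 685.5. Then (685.5 − 517.5)/88.6 = 1.90 and Φ(1.90 − 1.96) ≈ 0.47, close to the simulated 48.5%.

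**4. Conditional illustration of a lost effect.** This applies only if the pre sample is the week -1 draw. Assume a total ISA101b effect of 0.5 SD and no other change. If a share f is already present at week -1, the shift left to detect is 0.5(1 − f). For f = 0, 10%, 25% and 50%, power is 89%, 82%, 67% and 37%. If the pre sample is baseline or week -2, nothing is lost.

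**The case against.** The strongest reply is that item 2 is ambiguous rather than wrong. The wording can mean before and after the combination, and pre-vaccine material exists: the Table 10 baseline draw, a baseline biopsy before any protocol treatment (Appendix C), and section 9.4.3, which uses each patient's baseline as the control time point. This stands, and it rules out several stronger readings that a reader might infer:

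- That the reference sample is already post-vaccine. Item 2 does not say so; section 1.8 leans that way for blood but names no week -1 sample.
- That the interval always contains cisplatin and IMRT. Under the pre-dose assumption, week -1 to week 0 contains pembrolizumab only.
- That the test will reject when the vaccine does nothing, or will subtract an early effect. Both depend on shifts the documents do not give. They report no immune data one week after a first dose; the vaccine responses in Figure 1 follow two or three doses.

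A second reply is that section 9.4.8 plans an HPV16-specific ELISPOT to assess responses to ISA101b. That readout bears more directly on the vaccine, but the section names no time points, and section 1.7 reports that chemotherapy alone slightly raised the same response. It does not remove the confounding.

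A third is that the week -2 to week -1 pair tests one dose over a few days and omits doses 2 and 3, which section 5.4.2 times for maximal response. This is a real limit on what that contrast can show. It does not make a later interval attributable to ISA101b.

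**Conclusion.** The point holds in this form. On any choice of pre sample, a change measured to a post-pembrolizumab sample cannot be assigned to ISA101b, because no unvaccinated group exists and the interval contains at least one other agent expected to move the markers. This follows from the design and schedule and needs no simulation. The possible absorption of an early vaccine effect is conditional on a week -1 reference. The rejection range of about 5% to 89%, and the power figures, illustrate the risk and do not predict it: shifts, alpha, the number of pairs and normality are all assumed. Item 2 is a correlative analysis, so the primary PFS test, the toxicity summaries and the two monitoring rules are unaffected. This is a minor correction.

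**What to change.** Reword item 2 and remove the pre/post-pembrolizumab pairing.

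- **Reference, blood markers:** the pre-vaccine sample, meaning baseline, or week -2 if drawn before dosing.
- **ISA101b contrast:** paired Wilcoxon test of the week -1 sample, drawn before pembrolizumab, against that reference. Report it as the effect of ISA101b dose 1 alone. State that it covers about one week after a single dose (5 to 9 days, given the ±2 day window in section 5.2.3) and that a null result does not exclude a later or booster effect.
- **All later time points**, including those after doses 2 and 3: pair with the same reference and report as change under the combined regimen, not as the effect of ISA101b.
- **Table 10:** state whether the week -2 and week -1 draws precede that week's dose.
- **Tissue:** reconcile the optional biopsy weeks before defining pairs. Section 3.1 gives weeks -1 and 1; Table 10 and the Appendix C grid give weeks 1 and 2.

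The cost is a few sentences, with no new blood draw or visit. The price is a narrower vaccine claim, limited to a short interval after one dose.

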5.2.3 Dosing Schedule

Patients will receive three rounds of vaccination 3-4 weeks apart via two SC injections per vaccination round, after pembrolizumab treatment. Vaccination #1 will be administered 1 week before pembrolizumab (+/- 2 days).

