5.2.4 Order of Administration

When possible, ISA101b will be given on the same day of pembrolizumab for vaccines #2 and #3 (+/- 1 day). When administered on the same day, ISA101b should be given after the administration of pembrolizumab.

Patients should then be observed for 4 hours after the administration of ISA101b.

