8.2 Evaluations during treatment

8.2.1 Week -2 to 6 (During concurrent cisplatin-IMRT)

Weekly:

Note: The following assessments will be performed on the day of or the day prior to treatment administration.

- Targeted physical examination
- ECOG Performance Status
- Vital signs, including weight
- Toxicity assessment with attribution
- Update of concomitant medications
- Complete blood count, including platelets and differential
- Blood chemistries (may be obtained from whole blood or serum/plasma sample), including BUN, glucose, uric acid, lactate dehydrogenase, creatinine, electrolytes (K^+ , Na^+ , Cl^- , CO_2), calcium, Mg^{++} and liver function tests [bilirubin, AST (SGOT), ALT (SGPT), and alkaline phosphatase, total protein, albumin]
- Research biopsy of primary or nodal tumor tissue will be obtained at screening (mandatory), week 2 of Pembrolizumab (optional) and week 2 of IMRT (optional). Primary site biopsy is preferred, although a lymph node biopsy is acceptable in the event of inaccessible primary tumor. All effort should be made to biopsy the same site originally biopsied (i.e. primary tumor)

or pathologic lymph node), if accessible. Although the research biopsy may occur on any of the four days following cisplatin administration, it is preferred to occur on the first or second day following cisplatin administration. It is also preferred that the research biopsy precede the radiotherapy fraction on the day of research biopsy.

- Research blood on the same day as biopsy

8.2.2 Week 2 and Week 5:

Note: The following assessments will be performed every 3 weeks during concurrent cisplatin-IMRT, and may be performed on the day of or the day prior to treatment administration. It is recommended that research blood should be coupled to the standard of care blood draw, to minimize needle sticks to the patient.

- Thyroid function tests (TSH, FT4)
- Research blood
- Anti-thyroglobulin antibody, thyroid peroxidase antibody, thyroid stimulating immunoglobulin, and ANA tests

8.2.3 Week 7

- Targeted physical examination
- ECOG Performance Status
- Vital signs, including weight
- Toxicity assessment with attribution
- Update of concomitant medications
- Complete blood count, including platelets and differential

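### Item 2 of section 10.4 is labelled a test of the ISA101b effect, but its undefined pre/post pairs cannot isolate the vaccine on either reading of 'pre'

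*Combined protocol and SAP*

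**What the plan says.** Section 10.4, item 2, will "Estimate and test the effect of ISA101b using paired (pre/post pembrolizumab +/- ISA101b) values" of immune and inflammatory markers, with a Wilcoxon comparison. It names no draw as 'pre' or 'post'.

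On dosing, section 5 states: "The first ISA101b vaccine will be initiated 2 weeks prior to cisplatin-IMRT, and one week prior to the first dose of pembrolizumab". Section 5.2.3 gives the window: "Vaccination #1 will be administered 1 week before pembrolizumab (+/- 2 days". The sentence just before that one, however, describes the vaccinations as given "via two SC injections per vaccination round, after pembrolizumab treatment". For the later doses, section 5.2.4 says that, when possible, "ISA101b will be given on the same day of pembrolizumab for vaccines #2 and #3 (+/- 1 day".

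On sampling, Table 10 in section 9.1 and the list in section 9.3 schedule research blood at baseline and then at "Week -2, Week -1, CRT Weeks 0-3, Week 5, Week 7". Section 10 describes the trial as single-arm.

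**The concern.** The item promises an effect of ISA101b but words its pairs around pembrolizumab, and the two agents do not start together. A within-patient difference can be credited to one component only if that component alone changed between the two samples. Here three components start within two weeks: vaccine, then pembrolizumab, then cisplatin with radiation. Leaving 'pre' and 'post' undefined also leaves the choice of pair open until the data are in hand.

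This is the only item in the 10.4 list worded as an effect of ISA101b, in a trial whose purpose includes judging the addition of that vaccine. A reader of the results would take a significant test as evidence for the vaccine, and a null test as evidence against it. The pairs support neither conclusion.

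**Working it through.** **Inputs.** Dosing weeks come from section 5, Table 2 and Appendix C. Draw weeks come from sections 9.1 and 9.3. The ±2-day window comes from section 5.2.3. The plan gives no sample size, alpha or effect size for item 2, so there is no figure to reproduce.

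**Step 1: timeline.** Days after vaccine 1 = (week + 2) × 7.

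| Event | Week | Days after vaccine 1 |
|---|---|---|
| Vaccine 1 | -2 | 0 |
| Pembrolizumab 1 | -1 | 7 (7 ± 2 gives 5 to 9) |
| Cisplatin-IMRT starts | 0 | 14 |
| Vaccine 2 with pembrolizumab 2 | 2 | 28 |
| Vaccine 3 with pembrolizumab 3 | 5 | 49 |

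Vaccines 2 and 3 fall within a day of pembrolizumab, so no second vaccine-only interval occurs. Week -2 to week -1 is the only one, and blood is scheduled at both ends.

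**Step 2: what each pair contains.**
- 'Pre' = week -1, before pembrolizumab: one vaccine dose has already been given. The difference removes whatever response it had produced and adds pembrolizumab.
- 'Pre' = baseline, or week -2 before dosing: no vaccine is in the reference. Any 'post' draw after week -1 then contains vaccine plus pembrolizumab and, once chemoradiation has begun, cisplatin and radiation.
- Week -2 to week -1, both before dosing: vaccine 1 only. Item 2 does not name this pair.

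**Step 3: are the draws pre-dose?** The note on weekly assessments in section 8.2.1 reads "The following assessments will be performed on the day of or the day prior to treatment administration". Section 9.3 asks for blood before each pembrolizumab dose during radiation and before every third maintenance dose. Neither section states that the week -2 and week -1 research draws come before that day's treatment. A week -1 sample taken after the infusion would lose the vaccine-only pair.

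**Step 4: illustration on assumed effects.** Let δ be the vaccine effect in SD units of the paired difference, f the share of it already in 'pre', and c the shift from pembrolizumab and chemoradiation. The mean paired difference is δ(1 − f) + c. Rejection rates are for a two-sided 5% Wilcoxon signed-rank test with 45 normal pairs, SD 1 and 3,000 simulated trials. Monte Carlo error is at most √(0.25/3000), about 0.9 percentage points.

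| δ | f | c | Mean difference | Rejection |
|---|---|---|---|---|
| 0.4 | 0 | 0 | 0.40 | 72% |
| 0.4 | 0.25 | 0 | 0.30 | 48% |
| 0.4 | 0.5 | 0 | 0.20 | 24% |
| 0.5 | 0 | 0 | 0.50 | 89% |
| 0.5 | 0.25 | 0 | 0.375 | 67% |
| 0.5 | 0.5 | 0 | 0.25 | 36% |
| 0 | – | 0.3 | 0.30 | 49% |
| 0 | – | 0.5 | 0.50 | 89% |

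A mean difference of 0.30 arises from a vaccine effect of 0.4 with a quarter subtracted, or from no vaccine effect and a shift of 0.3 from the other treatments. The test cannot tell these apart.

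**Step 5: could chemotherapy shift these markers?** Section 1.7 reports, for the earlier cervical cancer trial, "Chemotherapy alone causes a slight increase in the spontaneous T cell response to HPV16 E6/E7". The rise was small and seen in a different disease without the present regimen. It shows that c need not be zero, but not how large it is.

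**The case against.** The wording of item 2 can also mean before and after the combination. Section 9.4.3 uses each patient's baseline as the reference for activated T cells, and the reference biopsy precedes all protocol treatment (Appendix C, note l). On that reading no vaccine response sits in 'pre'. This stands: a reader might infer from the pembrolizumab wording, and from the similar description in section 1.8, that 'pre' is the week -1 draw, but the documents do not settle it. It does not rescue the label, because a baseline-anchored difference is still a change on the combination.

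A reader might also infer that about a third of the vaccine effect is lost, since one dose of three precedes pembrolizumab. The documents do not support that. Section 5.4.2 times only doses 2 and 3 to the myeloid nadir to maximise response, section 1.7 describes weaker responses to vaccination not timed in this way, and week -1 falls only 5 to 9 days after a single dose.

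Nor do the documents show that the vaccine-only week goes unused across the plan. Table 10 assigns serum markers, immunophenotyping and functional assays to those draws, item 4 of 10.4 covers the sequential blood series, and section 9.4.8 plans an ELISPOT assay for responses to ISA101b. None of these names the contrast, and none excludes it.

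Finally, the week 0 draw may precede cisplatin and radiation, given the day-of or day-before allowance. It would still follow pembrolizumab.

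**Conclusion.** The point holds as a defect of definition and attribution. Under neither reading of 'pre' does item 2 estimate an effect of ISA101b, and it does not name the one interval that contains vaccine alone. This rests on the order in section 5, Table 2 and Appendix C, and on every patient being planned to receive both agents.

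The size of the bias cannot be derived from the documents. The percentages above depend on the assumed effects, test level and 45 pairs, and show only that both kinds of error are possible. The consequence is limited to an exploratory analysis. Within the 10.4 list, only item 1 has alpha allocated to it, and neither the primary PFS test nor a safety rule depends on item 2. The change should be made because the label would carry into the report, but the trial's main conclusion does not depend on it.

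**What to change.** In section 10.4, item 2:
1. Define 'pre' as the last sample before vaccine 1 (baseline, or week -2 before dosing), and name the 'post' draws.
2. Report later pre/post differences as change on the combined regimen, not as the effect of ISA101b.
3. For blood markers, add an exploratory vaccine-only contrast by paired Wilcoxon test: week -1 before pembrolizumab minus the pre-vaccine value.

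In sections 9.1 and 9.3, state that the week -2 and week -1 research draws are taken before that day's treatment. Separately, reconcile the two sentences of section 5.2.3 on the order of vaccine and pembrolizumab with each other and with section 5.

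The cost is text in 10.4 and one sampling instruction. No visit or draw is added. The limitation is that the new contrast sees about 5 to 9 days after one dose, whereas the earlier trial described in section 1.7 read responses three weeks after doses 2 and 3. It should therefore be added alongside the other readouts, not made the only vaccine readout, and the plan should say that a null result is not evidence of no vaccine response.
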